APPENDIX 2. ADVERSE EVENT COLLECTION: ELICITING, RECORDING, AND REPORTING

Table 14: Collection Period & Reporting Timeframe: Adverse Event & Other Safety Information Reporting

Event Type	Screening Period (including nutrition optimization and standardization), SAD cohorts, RD cohorts	Reporting Timeframe	Report to
SAE	
Start: From the time the subject signs the ICF
 
End: 28 days following the final dose of study drug or the EOS I (SAD cohorts) and EOS II or EOS III (RD cohorts) final study visit, whichever occurs later
 
Suspected related SAEs can be reported at any time following the EOS I/II visit
	Report all SAEs within 24 hours of site Investigator, designee or site personnel's knowledge of the event.	Electronic Data Capture (primary) Ultragenyx (back-up if Electronic Data Capture is down or not available) email: [contact] [contact]
AE	
Start: From the time the subject signs the ICF
 
End: 28 days following the final dose of study drug or the EOS I (SAD cohorts) and EOS II or EOS III (RD cohorts) final study visit, whichever occurs later
	Report all non-serious AEs within a target of 3 business days of site Investigator, designee or site personnel's knowledge of the event.	Electronic Data Capture
Pregnancy (includes Partner pregnancy)	
Start: From the time the subject signs the ICF
 
End: 28 days following the final dose of study drug or the EOS I (SAD cohorts) and EOS II or EOS III (RD cohorts) final study visit, whichever occurs later
	Report all pregnancies within 24 hours of site Investigator, designee or site personnel's knowledge of the event. Request consent to follow partner pregnancy (if applicable). Follow pregnancy until outcome is known (live birth, stillbirth, spontaneous abortion, elective termination, etc.).	Ultragenyx email: [contact] [contact]

AE, adverse event; EOS, end of study; ICF, informed consent form; RD, Repeat Dose; SAD, Single Ascending Dose; SAE, serious adverse event.

Table 15: Safety Contact Information

Global Drug Safety & Pharmacovigilance SAE and Pregnancy Reporting	Medical Monitor
[contact] email: [contact]	PPD [REDACTED] [name] [name] PPD [REDACTED]

Eliciting Adverse Events

A consistent methodology of non-directive questioning for eliciting adverse events (AEs) at all patient evaluation time points should be adopted. Examples of non-directive questions include:

“Since the last visit, has the patient experienced any health problems?”

“Have there been any new or changed health problems since you were last here?”

Recording AEs and SAEs

All AEs (ie, any new condition or worsening in severity or frequency of a preexisting condition) experienced by the patient within the protocol defined timeframes must be promptly documented on the case report form (CRF) and serious adverse event (SAE) form if applicable. This includes any AEs or SAEs considered associated with study protocol required procedures. For clinically significant worsening of a preexisting condition from Baseline the changes will be documented as AEs on the CRF. Clinical significance is defined as any variation in signs, symptoms, or testing that has medical relevance and may result in an alteration in medical care. The Investigator will continue to monitor the patient until the assessment returns to Baseline or until the Investigator determines that follow-up is no longer medically necessary.

The Investigator is responsible for evaluating all AEs, obtaining supporting documents, and ensuring documentation of the events is adequate. Details of the AEs must include severity, seriousness, relationship to study drug, duration (dates of onset and resolution), and outcome.

In addition, the Investigator should report any AE or SAE they are made aware of that occurs after the end of the study and that is believed to have a reasonable possibility of being associated with study drug.

Diagnosis versus Signs and Symptoms

If known, a diagnosis should be recorded on the CRF and SAE form (if applicable) rather than individual signs and symptoms. Whenever medically appropriate, the Investigator should group signs or symptoms that constitute a single diagnosis into a unifying event term. For example, record “liver failure” rather than jaundice, asterixis, and elevated transaminases, or record “upper respiratory tract infection” rather than cough, rhinitis, and sneezing. However, if a constellation of signs and/or symptoms cannot be medically characterized as a single diagnosis or syndrome at the time of reporting, each individual event should be recorded as an AE on the CRF and SAE form (if applicable). If a diagnosis is subsequently established, it should be reported as follow-up information by revising the CRF and SAE form (if applicable). Vague, nonspecific AE terms

such as “erythema,” “rash,” or “lump on head” should be avoided and more specific information should be provided, such as “erythematous macule on right leg,” “allergic dermatitis,” or “scalp cyst.”

Adverse Events Occurring Secondary to Other Events

In general, AEs occurring secondary to other events (eg, cascade events or clinical sequelae) should be identified by their primary cause. For example, if severe diarrhea is known to have resulted in dehydration, it is sufficient to record only diarrhea as the AE on the CRF and, if also serious, on the SAE form. However, medically significant AEs occurring secondary to an initiating event that are separated in time should be recorded as independent events on the CRF. For example, if a severe gastrointestinal hemorrhage leads to renal failure, both events should be recorded separately on the CRF.

Persistent or Recurrent Adverse Events

A persistent AE is one that extends continuously, without resolution between patient evaluation time points. Such events should only be recorded once in the CRF unless their severity increases. If a persistent AE becomes more severe, it should be recorded again on the CRF.

A recurrent AE is one that occurs and resolves between patient evaluation time points and subsequently recurs. All recurrent AEs should be recorded individually on the CRF.

Abnormal Laboratory Values

Only clinically significant laboratory abnormalities in the opinion of the Investigator are to be recorded as AEs on the CRF and SAE form (if applicable). For example, abnormalities that require study drug dose modification, discontinuation of study treatment, more frequent follow-up assessments, or further diagnostic investigation may be considered clinically significant by the Investigator.

If the clinically significant laboratory abnormality is a sign of a disease or syndrome (eg, alkaline phosphatase and bilirubin 5 × upper limit of normal (ULN) associated with cholecystitis), only the diagnosis (eg, cholecystitis) needs to be recorded on the CRF and the SAE form (if applicable).

If the laboratory abnormality can be characterized by a precise clinical term, the clinical term should be recorded as the AE or SAE. For example, an elevated serum potassium level of 7.0 mEq/L should be recorded as “hyperkalemia.”

Observations of the same clinically significant laboratory abnormality from visit to visit should not be repeatedly recorded as AEs on the CRF and SAE form (if applicable), unless their severity, seriousness, or etiology changes.

Reporting Serious Adverse Events

Any AE that meets SAE criteria must be reported to Ultragenyx or its designee within 24 hours of the site Investigator, designee or site personnel’s knowledge of the event. Regardless of causality, all SAEs must be reported during the time period. All SAEs must also be recorded in the patient’s source documentation and on the CRF. Copies of discharge summaries, consultant reports, and any other relevant documents should be provided with the SAE report when available.

If follow-up is obtained or requested by Ultragenyx and/or Medical Monitor, the additional information should be sent within 24 hours of knowledge.

Refer to Safety Contact Information for SAE reporting ([Appendix 2](#)).

Reporting of Pregnancy in Subject or Partner

For protocols requiring pregnancy reporting, any reported pregnancy of a subject or a subject's partner that occurs during participation in the study will be monitored for the full duration of the study and/or followed until the outcome of the pregnancy is known. In the event of a pregnancy in the partner of a subject, the Investigator should make every effort to obtain the female partner's consent for release of protected health information.

Pregnancy in a subject or subject's partner, complications of the pregnancy and the outcomes of pregnancy should be reported to the Ultragenyx or designee within 24 hours of site Investigator, designee or site personnel's knowledge of the event.

Pregnancies will be reported by completing and submitting Pregnancy Notification Form to Ultragenyx or designee.

Pregnancy outcomes will be reported by completing and submitting Pregnancy Outcome Form to Ultragenyx or designee.

The following pregnancy outcomes should always be classified as serious and reported to Ultragenyx or designee within 24 hours by completing and submitting the SAE and Pregnancy Outcome Form:

- Spontaneous abortion/Miscarriage
- Therapeutic abortion
- Ectopic pregnancy
- Fetal death/Still birth
- Molar pregnancy
- Birth defect/Congenital anomaly

Reporting Suspected Unexpected Serious Adverse Reactions

Ultragenyx or its designee will submit suspected unexpected serious adverse reactions (SUSARs) to appropriate Regulatory Authorities (including Competent Authorities in all Member States concerned), Institutional Review Boards/Independent Ethics Committees (IRBs/IECs), and Investigators as per local laws and regulations. Fatal and life-threatening SUSARs will be submitted no later than seven calendar days of first knowledge of the event and follow-up information submitted within an additional eight days. All other SUSARs will be submitted within 15 calendar days of first knowledge of the event.

The Investigator will notify the IRBs/IECs of SUSAR, in accordance with IRB/IEC requirements and local laws and regulations.

Non-SUSARs will be maintained in the Ultragenyx global safety database and provided in annual safety reports and/or other aggregate periodic summary reports to Regulatory Authorities and IRBs/IECs per local laws and regulations.

Reporting Urgent Safety Measures

Investigators are required to report any urgent safety measures taken to protect the safety or welfare of subject to Ultragenyx or its designee within 24 hours. Ultragenyx or its designee will inform the Regulatory Authorities, IRBs/IECs, and other investigators of any events (eg, change to the safety profile of Investigational Product (IP), major safety findings) that may occur during the clinical study that do not fall within the definition of a SUSAR but may affect the safety of subjects participating in the clinical study, as required, in accordance with applicable laws and regulations.

The Investigator will notify the IRBs/IECs of urgent safety measures, in accordance with IRB/IEC requirements and local laws and regulations. A copy of this notification must be provided to Ultragenyx or its designee.

Non-SUSARs will be maintained in the Ultragenyx global safety database and provided in annual safety reports and/or other aggregate periodic summary reports to Regulatory Authorities and IRBs/IECs per local laws and regulations.

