Subjects in SAD cohorts will be dosed at least 72 hours apart in each cohort, minimizing exposure to subjects if an early safety signal occurs. At least 2 weeks of safety data from at least 2 subjects in each SAD cohort will be reviewed prior to making a decision to proceed with the next cohort. Either at least 6 weeks of safety data from at least 4 subjects in a DB-RD cohort or 12 weeks of safety data from at least 3 subjects in an OL-RD cohort (whichever is available first) will be reviewed prior to making a decision to proceed with repeat dosing at the next dose level. The intervals between subjects and cohorts dosing were determined based on nonclinical studies, which showed that single-dose toxicities generally occurred soon after dosing, and that repeat-dose toxicities were observed after CCI. A detailed summary of nonclinical findings with UX053 is provided in the IB.

Study drug will be administered as an infusion over the course of at least 4 hours, with a slower rate of infusion for the first hour to minimize the risk of hypersensitivity or anaphylactoid-type reactions. The infusion rate may be slowed to minimize the risk of IRRs in individual subjects. Subjects will receive premedication at least 1 hour prior to infusion.

If a subject develops an infusion-related reaction that meets diagnostic criteria for anaphylaxis (Section 8.3.3), epinephrine should be administered as initial rescue medication. For all other hypersensitivity reactions \geq Grade 2 in severity suspected to be due to immune activation, dexamethasone should be the initial rescue medication (Section 9.5). The Medical Monitor must be notified if any rescue medication is used. If dexamethasone (or equivalent) is used as a rescue medication, premedication with dexamethasone (or equivalent) should be considered for that subject's subsequent infusions after discussion with the Medical Monitor.

A similar premedication regimen that includes dexamethasone is used for patisiran, a siRNA LNP treatment approved by the FDA in 2018 for the treatment of polyneuropathy of hereditary transthyretin-mediated amyloidosis in adults (ONPATTRO).

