- No evidence of vital sign instability or clinical instability in the opinion of the investigator.
- Any signs or symptoms of potential IRRs are resolving or resolved.

Guidance on signs and symptoms that subjects should be vigilant for upon discharge and how to proceed in the event that these signs and symptoms manifest are provided in Section [9.1.4](#).

In each SAD cohort, subjects will be dosed sequentially with review of safety laboratory data from the 24-hour time point prior to dosing of the next subject. Within SAD cohorts, dosing of individual subjects will occur at a minimum interval of 72 hours. For example, the second subject in a cohort receives their first dose after a minimum of 72 hours after the first subject in the same cohort received their first dose. Subjects within a given RD cohort can be dosed simultaneously. After the first dose, DB-RD subjects maintain a Q2W dosing regimen and OL-RD subjects maintain a Q4W dosing regimen.

Subjects may receive COVID-19 vaccines during participation in the study. To facilitate discrimination of UX053 IRRs and adverse effects of vaccine administration, vaccines should not be administered within 48 hours after the most recent administration of UX053 and until safety labs obtained have been reviewed and the subject has been assessed for any possible hypersensitivity reaction to the most recent dose of UX053 (Section [9.1.6](#)).

For the DB-RD cohort, the subjects, Investigators, and site staff will be blinded to the treatment. Due to the difference in the opacity of UX053 and placebo, an unblinded pharmacist will prepare the investigational product (IP) and an unblinded nurse will prepare the infusion before masking the infusion syringe and tubing with colored covers.

The full schedules of events for the SAD, OL-RD and DB-RD, cohorts are listed in [Table 4](#), [Table 5](#), and [Table 6](#), respectively. Additional details regarding the timing of assessments before, during, and following treatment infusion are provided in [Table 7](#) for vital signs and [Table 8](#) for PK samples.

Although they are eligible, it is expected that few patients with GSD IIIb, IIIc, or IIId will enroll. Subjects with GSD IIIb/c/d will participate in all assessments, including muscle imaging and function tests, and will be included in all safety analyses. Sensitivity analyses for cardiac and skeletal muscle endpoints may exclude patients with GSD IIIb/c/d as described in the SAP.

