7.1.4. Dose Rationale

The planned doses of UX053 (0.05, 0.10, and 0.20 mg/kg) aim to establish a safe dose of UX053 in adults with GSD III, as well as provide a preliminary PK and PD profile of UX053. These doses were chosen based on single-dose and repeat-dose pharmacology studies in mouse and dog models of GSD III, and RD toxicology and toxicokinetic studies in rats, cynomolgus monkeys, and Beagle dogs. The NOAEL in repeat-dose studies with 5 total doses of UX053 administered Q2W was **CCI** mg/kg in dogs, **CCI** mg/kg in rats, and **CCI** mg/kg in monkeys. The maximum tolerated dose (MTD) was **CCI** mg/kg in rats and **CCI** mg/kg in monkeys. The MTD in dogs is not known since higher doses were not evaluated with Q2W administration. The MTD in dogs with weekly dosing of UX053 is **CCI** mg/kg, but this short interval between doses is believed to promote an accumulation of toxicity that does not occur with Q2W dosing. Hence, the MTD in dogs may be greater than **CCI** mg/kg when UX053 is administered Q2W, but remains undetermined. **CCI**

Taken together, these PK and drug metabolism properties of the drug support 1:1 weight-based scaling from nonclinical species to humans, which is an approach endorsed by a cross-industry consortium of experts in oligonucleotide therapies, the Oligonucleotide Safety Working Group (Kornbrust, 2019; Marlowe et al., 2017). The FIH starting dose of 0.05 mg/kg is **CCI** less than the NOAEL in the most sensitive nonclinical species, the dog. The highest potential FIH dose of 0.30 mg/kg is **CCI** less than the dog NOAEL. Additional details regarding the use of weight-based scaling versus body-surface area scaling, as well as summaries of nonclinical studies with UX053 are available in the IB.

Sequential dosing with an interval of 72 hours between subjects' first dose within a cohort and a 2-week minimum review of data between cohorts was chosen to allow enough time to detect any potential TEAEs, including potential immune responses. In nonclinical studies, toxicities generally occurred soon after dosing and promptly resolved. The DB-RD cohorts will aim to achieve a steady state with Q2W dosing. The OL-RD cohorts will aim to evaluate a Q4W dosing regimen. Subjects will receive premedication prior to the treatment infusion to prevent hypersensitivity reactions, in line with previously established programs evaluating RNA therapeutics.

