8.3.3. Study Stopping Criteria

Study enrollment and any further administration of study drug for subjects already enrolled, will be paused and the DMC and regulatory authorities will be notified if, at any time during the study, any of the criteria listed below occur after UX053 administration:

- Death of a subject
- Any serious TEAE with a severity \geq Grade 3 that is assessed as related to study drug or study procedures by the Investigator or Ultragenyx
- Any TEAE with a severity \geq Grade 3 affecting the cardiopulmonary, renal, or neurological systems, regardless of relationship to study drug, pending a DMC safety review

- Anaphylaxis, as defined by the National Institute of Allergy and Infectious Diseases/Food Allergy and Anaphylaxis Network (NIAID FAAN) criteria ([Table 11](#)), pending a DMC safety review
- Increases in ALT or AST $> 2x$ from Baseline and $> 3x$ the ULN, accompanied by total bilirubin $> 2x$ ULN or INR > 1.5 , without findings of cholestasis (defined as serum ALP activity $< 2x$ ULN) and in the absence of a plausible alternate explanation
- Increases in serum concentrations of ALT or AST $> 2x$ from Baseline and $> 3x$ ULN with the appearance of fatigue, nausea, vomiting, right upper quadrant pain or tenderness, fever, rash, or eosinophilia ($> 5\%$ of total leukocytes)
- 3 subjects develop platelet counts $< 50,000$ per mm³ (or thrombocytopenia \geq Grade 3 in severity)
- 3 subjects develop INR > 1.5 (or INR increase \geq Grade 2 in severity)

In addition to the above criteria, the DMC may at any time recommend dose reduction or discontinuation of dosing for an individual subject or for all subjects (Section [9.1.5](#)). Regulatory authorities will be notified immediately if the study stopping criteria are met and study enrollment or dosing is halted.

Table 11: Clinical Criteria for Diagnosing Anaphylaxis

Anaphylaxis is highly likely when any one of the following 3 criteria are fulfilled:

1. Acute onset of an illness (minutes to several hours) with involvement of the skin, mucosal tissue, or both (eg, generalized hives, pruritus or flushing, swollen lips-tongue-uvula)
 
AND AT LEAST ONE OF THE FOLLOWING
 
a. Respiratory compromise (eg, dyspnea, wheeze-bronchospasm, stridor, reduced PEF, hypoxemia) b. Reduced BP or associated symptoms of end-organ dysfunction (eg, hypotonia [collapse], syncope, incontinence)

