- *Hospitalization signifies that the subject has been detained (usually involving at least an overnight stay) at the hospital or emergency ward for observation and/or treatment that would not have been appropriate in the physician's office or outpatient setting. When in doubt as to whether 'hospitalization' occurred or was necessary, the AE should be considered serious.*
 - *AEs requiring hospitalization should be considered SAEs. Hospitalization planned prior to study enrollment (eg, for elective surgery or routine clinical procedures) that are not the result of AE (eg, elective surgery for a pre-existing condition that has not worsened) need not be considered AEs or SAEs. If anything untoward is reported during the procedure, that occurrence must be reported as an AE, either 'serious' or 'non-serious' according to seriousness criteria described above.*
- Disability/Incapacity
 - *An AE is disabling or incapacitating if it results in substantial and/or permanent disruption of the subject's ability to carry out normal life functions.*
- Congenital anomaly/birth defect not present at screening
- Important Medical Events that may not result in death, be immediately life-threatening, or require hospitalization may be considered serious when, based upon appropriate medical judgment, they may jeopardize the patient or subject and may require medical or surgical intervention to prevent one of the criteria listed in the definition. Examples of such events are:
 - Intensive treatment in an emergency room or at home for allergic bronchospasm
 - Blood dyscrasias that do not result in inpatient hospitalization
 - Development of drug dependency or drug abuse
 - Emergency room visits requiring medical intervention related to the study or study procedures, where subjects, due to hospital capacity, could not be admitted (eg, due to coronavirus 2019 [COVID-19])

Participation-emergent Adverse Events

These events may be related to study participation or biological specimen collection and will be reported by the Investigator and noted as such in the case report form (CRF) as related to study intervention.

Overdose

An overdose is defined as a known deliberate or accidental administration of investigational drug, to or by a study subject, at a dose above that which is assigned to that individual subject according to the study protocol. All cases of overdose (with or without associated AEs) will be documented in the CRF.

Assessment of Severity

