- Mild (Grade 1): Subject has awareness of signs or symptoms, but easily tolerated and are of a minor irritant type, causing no loss of time from normal activities. Symptoms do not require therapy or a medical evaluation; signs and symptoms are transient.
- Moderate (Grade 2): Events introduce a low level of inconvenience or concern to the subject and may interfere with daily activities, but are usually improved by simple therapeutic measures; moderate experiences may cause some interference with functioning.
- Severe (Grade 3): Events interrupt the subject's normal daily activities and generally require systemic drug therapy or other treatment; they are usually incapacitating.

- Life-threatening (Grade 4): Events that place the subject at immediate risk of death or are disabling.
- Death (Grade 5): Events that result in death.

Note: The term "severe" is often used to describe the intensity (severity) of a specific event (as in mild, moderate, or severe myocardial infarction); the event itself, however, may be of relatively minor medical significance (such as severe headache). This is not the same as "serious" which is based on subject/event outcome or action criteria and is usually associated with events that pose a threat to a subject's life or functioning. Seriousness (not severity) serves as a guide for defining regulatory reporting obligations.

Assessment of Causality

The Investigator will make a causality assessment about the relationship of each AE to study drug. Treatment-related conditions must be distinguished from disease-related conditions.

The Investigator should determine the causality (relation to the study drug) based on his/her clinical experience and on the information given in the Investigator's Brochure. The causal relationship of all AEs to the study drug will be judged as either related (which includes possibly, probably or definitely related) or not related (which includes unlikely or doubtfully related).

To ensure consistency of AE and SAE causality assessments, Investigators should apply the following general guideline:

- **A related** causal relationship means that there is at least a reasonable possibility that the event is caused by the study drug or the research procedures. There may be a reasonable possibility of a causal relationship between study drug/Investigational Product (IP) and the AE when:
 - The event follows a reasonable temporal sequence post IP administration

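### A non-serious Grade 3 event that pauses the study under Section 8.3.3 has only a 3-business-day reporting target, so the next SAD subject, at another site, may be dosed at 72 h before the sponsor hears of it

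*Protocol*

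**What the plan says.** Four provisions bear on the point.

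- **Pause rule.** Protocol Section 8.3.3 halts enrollment and all further dosing for any Grade 3 or higher TEAE "affecting the cardiopulmonary, renal, or neurological systems, regardless of relationship to study drug". It sets no seriousness condition, whereas the preceding bullet in the same list is limited to serious TEAEs.
- **Reporting clock.** Table 14 (Appendix 2) requires SAEs within 24 hours of site knowledge. For other events it says "Report all non-serious AEs within a target of 3 business days", through electronic data capture, with no exception for an event that meets a stopping criterion.
- **Stagger.** Section 7.1 sets a minimum of 72 hours between subjects in a SAD cohort. It says that "subjects will be dosed sequentially with review of safety laboratory data from the 24-hour time point prior to dosing of the next subject". Adverse event review is not named.
- **Purpose of the stagger.** Section 7.1.4 says that the interval, with the 2-week review between cohorts, "was chosen to allow enough time to detect any potential TEAEs, including potential immune responses". Section 5.5 says "Subjects in SAD cohorts will be dosed at least 72 hours apart in each cohort, minimizing exposure to subjects" in the event of an early safety signal.

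Section 7.1.1 plans about 10 sites, so consecutive subjects in a cohort may be at different sites.

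**The concern.** The stagger protects the second subject only if news of the first subject's event arrives in time. Severity triggers the pause, but seriousness sets the speed of the report. Appendix 1 itself says that severe and serious are different things and gives a severe headache as a severe event of minor medical significance. A site could therefore hold an event that meets a pause criterion, report it on target, and still be too late for a subject dosed elsewhere at 72 h. At stake is one further first-in-human exposure that the protocol meant to hold back.

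**Working it through.** The plan gives no figure to reproduce, so the check is calendar arithmetic.

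**Inputs.** Minimum interval 72 h (Section 7.1). Infusion of at least 4 h, then 24 h of observation, so discharge from about 4 + 24 = 28 h (Section 7.1). Clock of 3 business days or 24 h from site knowledge (Table 14). Assumed: infusion starts at 08:00, Monday to Friday are business days, no holidays.

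**Formula.** Latest on-target report, in hours after dosing = hours to site knowledge + reporting allowance. Two readings of 3 business days were used:

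- A: three full business days after knowledge.
- B (stricter): the day of knowledge is business day 1, and the deadline is 17:00 on day 3.

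Example: dose Tuesday 08:00, event known Wednesday 12:00 (28 h). Under A, three business days run to Monday 12:00, which is 120 h later: 28 + 120 = 148 h. Under B, the deadline is Friday 17:00: 72 + 9 = 81 h.

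| Dose day | Known at 4 h: A / B | Known at 28 h: A / B |
|---|---|---|
| Mon | 76 / 57 | 100 / 81 |
| Tue | 76 / 57 | 148 / 81 |
| Wed | 124 / 57 | 148 / 129 |
| Thu | 124 / 105 | 148 / 129 |
| Fri | 124 / 105 | 124 / 129 |
| Sat | 100 / 105 | 100 / 105 |
| Sun | 76 / 81 | 100 / 81 |

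**Known at 28 h.** Every entry is later than 72 h, by 100 − 72 = 28 h to 148 − 72 = 76 h under A, and by 81 − 72 = 9 h to 129 − 72 = 57 h under B. If dosing is on weekdays only, the first slot after a Wednesday dose is Monday at 120 h, and after a Thursday dose Monday at 96 h. The lags for Monday to Friday dosing are then 28, 76, 28, 52 and 52 h under A, and 9, 9, 9, 33 and 57 h under B.

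**Known at 4 h.** Under A the report falls at 76 to 124 h. Under B it falls at 57 h for Monday to Wednesday dosing, before the 72 h slot, and at 81 to 105 h otherwise.

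**With a 24-hour clock.** Known at 4 h: 4 + 24 = 28 h. Known at 28 h: 28 + 24 = 52 h, which is 20 h before the slot. The margin is zero for an event known at 72 − 24 = 48 h. Events first known later need a check made at the time of the next dose.

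**Other routes by which the sponsor might hear sooner.**

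- Section 7.1 has the sponsor notify the DMC immediately, but that duty starts only when the sponsor knows.
- Rescue medication must be notified to the Medical Monitor (Sections 7.1 and 8.3.2). No deadline is stated, and an event managed without rescue medication is not reached.
- Appendix 2 requires urgent safety measures to be reported within 24 hours, but only if such a measure is taken. It also asks for prompt CRF documentation, with no time beyond the Table 14 target.
- The 24-hour laboratory review would mainly show renal events. In the SAD schedule (Table 4), troponin I, CK-M/B and BNP are listed at Screening and Baseline only. The Day 1 ECG is not part of the stated pre-dose review.

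None of these gives a timed site-to-sponsor notice for a non-serious event that meets a pause criterion.

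**The case against.** The strongest reply is that few events fall in the gap.

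- Section 7.1 bars discharge while there is clinical or vital sign instability or unresolving infusion-reaction signs. A subject with an active Grade 3 event at 28 h would normally be kept. Appendix 1 makes prolonged hospitalization an SAE, and where there is doubt whether hospitalization "occurred or was necessary, the AE should be considered serious". It adds that "Important Medical Events that may not result in death, be immediately life-threatening, or require hospitalization may be considered serious when" medical judgment sees jeopardy to the subject. Such events go on the 24-hour clock.
- Section 11.4 classes every AE during infusion or within 4 hours after it as an infusion-related reaction. At Grade 3 or higher, Table 10 then calls for dexamethasone and no redosing, which brings in the Medical Monitor.
- Table 14 is a data-entry target and 72 h is a minimum. The pause in Section 8.3.3 attaches to the event, not to its entry in the database. Reviewing the previous subject's laboratory data already implies some contact before the next dose.
- The DMC Charter and site manuals are not among the documents and may set faster notice.

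The first two points stand and set the size of the concern. What remains are Grade 3 events that have resolved or are stable at discharge, or that first become known afterwards, and are judged non-serious. The third point shows that a late report is possible, not certain. It does not supply the missing clock, because a pause across sites cannot begin until someone outside the first site knows. The fourth cannot be settled from the protocol and SAP.

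**Conclusion.** The mismatch is in the text and deserves a cheap correction, in narrow form. For a non-serious Grade 3 event known at 28 h, with the next subject at another site, a site that meets its target may report 9 to 76 h after the 72 h slot across both readings. An event known at 4 h may be reported before or after that slot, depending on the weekday and the reading. The result assumes an 08:00 start, no holidays and dosing of the next subject at or near the first permitted time.

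A reader might infer more in three ways, and the documents support none of them.

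- That Grade 3 or higher events in general can go unreported for days: most that are still active at 28 h would be SAEs, due by 52 h.
- That a subject was in fact dosed after an unreported event: no dosing dates, site allocation or events are given.
- That the same comparison holds in the repeat-dose cohorts: Section 7.1 lets those subjects be dosed simultaneously, so there is no 72-hour stagger to defeat.

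SAP Section 8 says the study terminated, for administrative reasons, after 4 subjects in each of Cohorts 1S and 2S. The point therefore matters only if this text is reused.

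**What to change.** 1. **Table 14, with a cross-reference from Section 8.3.3.** Require notice to the Medical Monitor within 24 hours of site knowledge, regardless of seriousness, of any event that meets or may meet a study stopping criterion in Section 8.3.3 or a no-redosing criterion in Section 8.3.2. The latter means the three bullets that bar redosing and Grade 3 or higher infusion-related reactions. Leave out the routine redosing laboratory limits and Grade 1 to 2 infusion reactions, which would bring in many ordinary out-of-range values and mild events. Table 14 already has a 24-hour row that does not depend on seriousness, for pregnancy.
2. **Section 7.1.** Add to the existing 24-hour laboratory review that, before the next SAD subject is dosed, the Medical Monitor confirms with the sites of already-dosed subjects in the cohort that no such event is known or pending. This also covers events first known after 48 h.

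The stopping criteria and the 72-hour stagger stay unchanged.

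The cost is wording in three places, a few more 24-hour reports, and one confirmation per SAD dose after the first in each cohort: 3 × (2 − 1) = 3 at the planned minimum, or 2 × (4 − 1) = 6 for the cohorts as enrolled. No visits or procedures are added.
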